## **6.2 EAE Reporting**

After the protocol-defined AE reporting period, unless otherwise noted, only SUSARs as defined in Version 2.0 of the EAE Manual will be reported to DAIDS if the study staff become aware of the events on a passive basis (from publicly available information).

Requirements, definitions, and methods for expedited reporting of AEs are outlined in Version 2.0 of the DAIDS EAE Manual, which is available at <https://rsc.niaid.nih.gov/clinical-research-sites/manual-expedited-reporting-adverse-events-dais>.

The study agents for the purposes of EAE reporting are: Oral CAB 30 mg oral tablet; CAB LA 3 mL (600 mg) intramuscular (IM) injectable suspension.

### **6.2.1 Reporting to DAIDS**

The DAIDS Adverse Event Reporting System (DAERS), an internet-based reporting system, must be used for EAE reporting to DAIDS. In the event of system outages or technical difficulties, EAEs may be

submitted via the DAIDS EAE form. For questions about DAERS, please contact [contact]. Site queries may also be sent with the DAERS application itself.

If the DAERS website or site internet is non-functional, sites will submit expedited AEs by documenting the information on the current DAIDS EAE form. This form is available on the DAIDS RSC website: <https://rsc.niaid.nih.gov/clinical-research-sites/paper-eae-reporting>. For questions about EAE reporting, please contact the DAIDS RSC at [contact].

### **6.2.2 Reporting Requirements for This Study**

The SAE Reporting Category, as defined in Version 2.0 of the DAIDS EAE manual, will be used for this study (the definition of an SAE is also included in the manual).

In addition to SAEs, sites will report in an expedited manner the following results:

- ALT  $\geq$  3xULN AND total bilirubin  $\geq$  2xULN (must be both in order to require expedited reporting)
- Any seizure event

These reporting requirements are for each study participant from Enrollment (Week 0) until follow-up in the study ends. After this time, sites must report serious, unexpected, clinical suspected adverse drug reactions if the study site becomes aware of the event on a passive basis, i.e., from publicly available information.

The study agents for the purposes of EAE reporting are: Oral CAB 30 mg oral tablet; CAB LA injectable suspension (200 mg/mL).

In addition to submitting EAE information to the DAIDS Safety Office via DAERS, the site investigator may be required to submit AE and EAE information to local regulatory agencies or other local authorities.

Information on Grade 1 and higher AEs will be included in reports to the US FDA, and other government and regulatory authorities as applicable. Site staff will report information regarding AEs to their IRB in accordance with all applicable regulations and local IRB requirements.

### **6.3 Safety Monitoring**

Two hundred and thirty (n=230) healthy participants from completed studies have received single or repeat doses of CAB LA in Phase 1 studies at doses ranging from 100-800 mg administered as single or split IM or SC injections. In the Phase 1 program, to date there have been no drug-related Grade 3 or Grade 4 clinical AEs and only one participant has been withdrawn from dosing due to mild and transient rash. Injection site reactions (ISR) occurred in the majority of participants following IM (77% with any ISR) dosing, however, the reactions were mild and moderate (overall ISR Grade 2: 14% in IM without any Grade 3 or 4 ISRs). ISRs related to CAB LA injection were common but generally mild (IM: 86%, SC: 99%) with no Grade 3 ISR AEs in Phase 1 studies. The most frequent ISRs for IM dosing were pain (71%), erythema (9%) and nodules (7%). Median IM ISR durations were approximately 5 days for pain and erythema, and approximately 22 days for nodules.

AEs were reported at all studied doses. The most frequent (>5%) non-ISR AEs were headache (overall rate of 16%: 10% in oral and 27% in LA) which occurred more frequently than in placebo subjects (11%) and upper respiratory tract infection (overall rate of 6%: 2% in oral and 12% in LA) versus none in placebo subjects. CAB was well tolerated across all studies with an overall incidence of 13% of any drug-related AEs and few drug related withdrawals.

The ECLAIR study, conducted at 10 US sites, screened 205 individuals in order to enroll and randomize 127 HIV-uninfected low-risk men. Participants received daily oral CAB 30 mg or daily oral placebo in a randomized 5:1 ratio during the 4-week oral lead-in phase. One participant randomized to active study product (oral CAB and CAB LA) withdrew prior to the oral lead-in due to being incarcerated. During the oral lead-in, 11 participants withdrew prior to their first injection, all of whom were randomized to CAB LA, seven for AEs and four for other reasons. Ninety-four (94) participants received at least one injection of CAB LA 800 mg and 21 participants received at least one injection of placebo. Of those that started injections 95% (20 of 21) of those randomized to placebo and 93% (87 of 94) of those randomized to CAB LA completed all three injections. The participant in the placebo arm who did not complete all three injections reached a protocol-defined stopping criteria (he acquired HIV infection after his second injection). Four participants on the CAB LA arm withdrew after their second injection, citing injection tolerability as a primary reason. Three other participants discontinued study participation after receiving injections for non-AE and non-injection-related reasons.

Fifteen participants experienced a Grade 1 or higher ALT and 14 experienced a Grade 1 or higher AST. There were no Grade 3 or 4 ALT elevations. AE events leading to withdrawal included transient neutropenia (three participants), transiently elevated CPK (three participants), and fatigue (one participant). Two SAEs were reported, one deep vein thrombosis on placebo that was considered possibly drug-related and one appendicitis on CAB LA that was not considered drug related. Eighteen participants reported Grade 3 ISR pain.

Grade 4 treatment emergent CPK elevations with concomitant AST and/or ALT elevations were noted in four participants at the Week 4 visit, leading to early withdrawal in three participants. One of the four participants described a new rigorous exercise regimen prior to the Week 4 study visit; a second of these events resolved despite ongoing exposure to study product. All four Grade 4 abnormalities were resolving at one-week follow-up visits and have subsequently returned to normal off study product.

Close cooperation between the Protocol Chair, study site Investigator(s), DAIDS Medical Officer, LOC Clinical Research Manager, SDMC Biostatistician, SDMC Clinical Affairs Staff, HPTN LC, and other study team members will be necessary in order to monitor participant safety and to respond to occurrences of toxicity in a timely manner.

The study site Investigators are responsible for continuous close monitoring and management of AEs. Sites are required to have detailed SOPs describing methods for AE reporting and toxicity management to ensure that AEs are reported and managed in accordance with the protocol and for alerting the CMC (outlined below) if unexpected concerns arise.

A sub-group of the Protocol Team, including the Protocol Chair and Co-Chair, DAIDS Medical Officer, and other site investigators will serve as members of the CMC. The CMC provides support to sites regarding individual participant clinical management (e.g., questions related to eligibility, toxicity management, clinical holds of study drug, etc.).

## **6.4 Clinical Data Review**

A multi-tiered safety review process will be followed for the duration of this study. The study site investigators are responsible for the initial evaluation and reporting of safety information at the participant level, and for alerting the CMC if unexpected concerns arise.

Participant safety data is also monitored by the SDMC Clinical Affairs staff who review incoming safety data for completeness and consistency on an ongoing basis. Events identified as questionable, inconsistent, or unexplained will be queried for verification.

AE reports submitted in an expedited manner to the DAIDS Safety Office will be forwarded to the DAIDS Medical Officer for review and possible reporting to the FDA as a Safety Report.

This study will be monitored by a NIAID Data and Safety Monitoring Board (DSMB), along with the parent protocols, which will meet at least annually to review safety and efficacy data. More frequent or *ad hoc* reviews of safety data may be conducted by the DSMB as needed.

## **6.5 Social Harms and Social Benefits Reporting**

It is possible that participants' involvement in the study could become known to others, and that a social harm may result (i.e., because participants could be perceived as being HIV-infected or at "high risk" for HIV infection). For example, participants could be treated unfairly, or could have problems being accepted by their families and/or communities. These are social harm events. Social harms events are those negative events that a participant reports as affecting them as a result of being involved in a research study, not the researcher's opinion of how they perceive an event has affected a participant. A social harm that is reported by the participant and judged by the IoR/designee to be serious or unexpected will be reported to the responsible site's IRBs at least annually, or according to their individual requirements.

Social harms and benefits will be collected and reported on CRFs during regular visits. In the event that a participant reports a social harm, every effort will be made by study staff to provide appropriate care and counseling to the participant as necessary, and/or referral to appropriate resources for the safety of the participant. Each site will provide such care and counseling in accordance with standardized guidance in the SSP Manual. While maintaining participant confidentiality, study sites may engage their Community Advisory Board in exploring the social context surrounding instances of social harms, to minimize the potential occurrence of such an impact. In addition to social harms, any benefits of study participation, which are outcomes reported by the participant as a benefit to them as a result of being in the study (e.g., improvement in relationships), will also be collected and reported into the database.

## **7.0 STATISTICAL CONSIDERATIONS**

### **7.1 Review of Study Design**

This is a single arm, open label, safety, tolerability, and acceptability study of CAB LA for prevention of HIV-acquisition in sexually-active, HIV-uninfected adolescents (below aged 18 years old at time of enrollment).

The study includes a 5-week oral CAB 30mg QD safety lead-in followed by a series of 5 intramuscular (IM) injections of 3 mL (600 mg) CAB LA administered at 8-week intervals after a 4-week loading dose (injections at weeks 5, 9, 17, 25 & 33). Follow up on study product (oral and injectable) will occur for 34 weeks. All participants who have received at least one injection will be followed for 48 weeks after their last injection. Waning levels of cabotegravir (the PK tail) will be covered with locally sourced oral Tenovovir/Emtricitabine (TRADE NAME: TDF/FTC, TRUVADA®) for daily use or continued use of CAB LA for 48 weeks.

The sample size for this study will be set to enroll approximately 50 participants. The sample size for this protocol (n=50) is the number of participants agreed upon by the industry sponsor and regulators in order to provide supplementary safety and behavioral data on adolescents in collaboration with the HPTN 083 and HPTN 084 adult trials. The primary aims of the study are focused on safety, tolerability, and acceptability of this long-acting product.

Finally, in-depth qualitative interviews will be conducted with 10 participants (total, across all sites) after Week 34 to explore issues of acceptability and preference for oral tablets and/or injections. Additionally, up to 10 parents/guardians of participants (total, across all sites) will be asked to participate in in-depth interviews to explore facilitators and barriers to adolescent enrollment in biomedical clinical trials.

## **7.2 Endpoints**

### **7.2.1 Primary Endpoints**

- Safety endpoint: Proportion of participants experiencing any Grade 2 or higher clinical adverse events (AEs) and laboratory abnormalities among participants who receive at least one injection of CAB LA
- Tolerability endpoint: Proportion of participants who receive at least 1 injection and who discontinue receiving injections prior to the full course of injections due to intolerability of injection, frequency of injections or burden of study procedures
- Acceptability endpoint: Proportion of participants who complete all scheduled injections and proportion of participants who receive at least one injection whom would consider using CAB LA for HIV prevention in the future

### **7.2.2 Secondary Endpoints**

- Plasma CAB pharmacokinetics
- Proportion of participants experiencing Grade 2 or higher clinical AEs and laboratory abnormalities in the oral phase and the aggregate over the entire study period
- Proportion of injection visits that occurred “on-time”
- Change from enrollment of self-reported sexual behavior (number of sexual partners, increased episodes of unprotected anal intercourse) during the study period

### 7.3 Sample Size

The sample size for this protocol (n=50) is the number of participants agreed upon by the industry sponsor and regulators in order to provide supplementary safety and behavioral data on adolescents in collaboration with the HPTN 083 and HPTN 084 adult trials. The goal of the safety evaluation for this study is to identify safety concerns associated with CAB LA.

Since each of the primary endpoints is a proportion, Table S1 shows the precision (confidence interval width) that will be obtained for each endpoint with a sample size of 50.

Table S1. Width of 95% confidence interval for estimated proportion as a function of the true proportion, assuming a sample size of 50.	
True proportion	Width of 95% CI
0.1	± 0.083
0.2	± 0.11
0.3	± 0.13
0.4	± 0.14
0.5	± 0.14

The study will recruit sufficient participants to ensure that at least 50 participants progress to the injection phase.

### 7.4 Randomization

There is no treatment randomization due to this study being a single arm, open label trial.

### 7.5 Blinding

Participants and site staff will be unblinded throughout the trial.

### 7.6 Data and Safety Monitoring Analysis

#### 7.6.1 Study Monitoring Committee

NIAID DSMB oversight is planned for this study. Monitoring guidance will be detailed in a separate Interim Monitoring Plan.

In addition, approximately every six months the HPTN SMC will conduct interim reviews of study progress, including rates of participant accrual, visit retention, and completion of primary and main secondary endpoint collection. The frequency and content of SMC reviews will be determined prior to the start of the study as outlined in the HPTN Manual of Procedures (MOP).

## **7.7 Primary Analyses**

All participants who receive at least one injection will contribute to the primary analyses. When the use of descriptive statistics to assess group characteristics or differences is required, the following methods will be used: for categorical variables, the number and percent in each category; for continuous variables, the mean, median, standard deviation, quartiles and range (minimum, maximum).

### **7.7.1 Safety Endpoints**

The primary safety analysis will include Grade 2 or higher clinical and laboratory events that occur from the initial injection to 48 weeks after the last injection among participants who receive at least one injection.

To assess safety, the number and the percent of participants experiencing each safety endpoint will be tabulated. Each participant will contribute once in each category (for example, only for the highest severity AE for each participant) for the calculation of event rates. Exact binomial confidence intervals will be calculated for each safety endpoint.

### **7.7.2 Injection Site Reaction (ISR)**

The number and percentage of participants experiencing each type of injection site reaction sign or symptom will be tabulated by severity. For a given sign or symptom, each participant's ISR will be counted once under the maximum severity for all injection visits as well as by each successive injection.

In addition, we will report the proportion of injections (over all participants) that resulted in an ISR. A 95% CI (using a robust variance) will be computed.

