### **2.3 Study Design and Overview**

We propose a single arm, open label, safety, tolerability, and acceptability study ( $n=$  approximately 50) in sexually-active, healthy adolescents assigned male sex at birth.

Study participation includes, Step 1: a 5-week oral CAB 30mg QD safety lead-in followed by a series of 5 intramuscular (IM) injections of 3 mL (600 mg), administered at 8-week intervals after a 4-week loading dose (injections at weeks 5, 9, 17, 25 & 33) in Step 2. Adherence support strategies (e.g., counseling, reminders, pill cases) will be included to support pill-taking during the first five weeks and to support retention during the injectable phase. A safety visit will follow each injection to ascertain pharmacokinetic-peak safety data, including injection site reactions. Step 3: a blood draw visit, the +8

Week Visit, will follow the last Step 2 injection to monitor CAB drug levels. All participants who have received at least one injection will be followed for 48 weeks after their last Step 2 injection. Waning levels of cabotegravir (the PK tail) will be covered with locally sourced oral Tenofovir/Emtricitabine (Trade name: TDF/FTC, Truvada®) for daily use for 48 weeks or the participant can opt to continue CAB LA injections for the duration of Step 3. Behavioral and acceptability data will be collected via computer-assisted self-interview (CASI).

Participants who discontinue study product during Step 2 for any reason other than HIV infection or AE occurrence will be transitioned to open label Tenofovir/Emtricitabine (Trade name: TDF/FTC, Truvada®) for 48 weeks.

Finally, in-depth qualitative interviews will be conducted after the end of Step 2 (Week 34) with 10 participants (total, across all sites) to explore issues of acceptability and preference for oral tablets and/or injections. Additionally, up to 10 parents/guardians of participants (total, across all sites) will be asked to participate in in-depth interviews to explore facilitators and barriers to adolescent enrollment in biomedical clinical trials as well as parental acceptability of injectable prevention products for youth.

As previously mentioned, we have chosen an unblinded, single arm trial because it is most developmentally-appropriate for adolescents and minimizes participant and staff burden, while also offering a more streamlined visit schedule than the parent protocols and, hopefully, promoting study drug adherence.

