#### **5.6 Step 2, Injection Phase: Safety Visits**

##### **Injection Phase Safety Visits at Week 6, 10, 18, 26, and 34**

During the injection phase of the study, all participants will have brief safety visits one week after each injection. Blood will also be collected at these visits to monitor drug levels of CAB. A three-month supply of Tenofovir/Emtricitabine [TRADE NAME: TDF/FTC, TRUVADA®] will be provided at Week 34, if the participant chooses oral follow-up (vs. CAB LA).

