**12.4 APPENDIX IV. SCHEDULE OF EVALUATIONS – FOLLOW-UP PHASE (STEP 3-INJECTION)**

WEEKS SINCE LAST INJECTION	Wk +8	Wk +16	Wk +24	Wk +32	Wk +40	Wk +48	Early Discontinuation
ADMINISTRATIVE, BEHAVIORAL, REGULATORY							
Locator information	X	X	X	X	X	X	X
HIV prevention & risk reduction counseling	X	X	X	X	X	X	X
Condoms per local SOC	X	X	X	X	X	X	X
Behavioral/Acceptability assessment (CASI)		X	X	X	X	X	X
CLINICAL EVALUATIONS & PROCEDURES							
Qualitative interviews continue (approximately)		X	X				
Medical history  , concomitant medications, targeted physical exam		X	X	X	X	X	
Hep B vaccination (if needed) 							X
Blood collection	X	X	X	X	X	X	
Urine collection			X			X	X
Rectal swab collection			X			X	
Injections (CAB LA)	X	X	X	X	X	X	X
ISR evaluation	X	X	X	X	X	X	X
Adherence counselling	X	X	X	X	X	X	X
LOCAL LABORATORY EVALUATIONS & PROCEDURES							
HIV testing 	X	X	X	X	X	X	X
CBC with differential			X			X	
Chemistry testing 	X		X			X	X
Liver function testing 	X		X			X	X
Syphilis testing			X				X
GC/CT testing (urine, rectal, and oral pharyngeal swabs)			X			X	X
Plasma storage 	X	X	X	X	X	X	
DBS storage		X	X		X	X	
HBsAb and HBcAb 						X	X
HCVAb						X	X

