Impact on Creatinine	CAB	Regulatory Interest, Therapeutic Area

Confidential

All proprietary rights reserved

Page 22 of 27

Hyperglycemia/new onset diabetes mellitus	CAB	Observation from 083, Class
---	-----	-----------------------------

Common ISR adverse events are defined by MedDRA preferred terms including injection site pain, injection site induration, injection site nodules and preferred terms of any other ISR exceeding the threshold as specified in the ADRG. ISRs will be explored regardless of IP relationship.

Each one of the AESIs described in Table 3 will be explored via the data listings in more detail. Listings will summarize Adverse events that occurred during Step 1 and/or Step 2 of the study and will contain information to assess the following.

Event Characteristics: The characteristics of all event occurrences during the post-baseline period will look at event characteristics (serious, drug-related, leading to withdrawal, or Grade 3/4, fatal), number of events per participant, outcome, maximum grade or intensity and action taken.

Time to First Event (TTFE) and Duration of Events: Time of onset and duration of event will be provided.

In addition, Pyrexia Plus includes PT: (Chills – 10008531, Feeling of Body Temperature Change - 10061458, Feeling Hot - 10016334, Body Temperature Increased - 10005911, Pyrexia - 10037660, Influenza Like Illness - 10022004, Fever – 10016558) events will be looked at in relation to timing of previous injection.

No formal summaries or statistical comparisons are planned for AESI.

15. APPENDIX B – Variable Definitions

1. CES-D-10 (score/categories)

Create a score based on 10 items below (in CASI questionnaire):

In the list below, please indicate how often you have felt this way during the past week by ticking the appropriate box for each question:

1. I was bothered by things that usually don't bother me.
2. I had trouble keeping my mind on what I was doing.
3. I felt depressed.
4. I felt that everything I did was an effort.
5. I felt hopeful about the future.
6. I felt fearful or afraid.
7. My sleep was restless.
8. I was happy.
9. I felt lonely.
10. I could not "get going", I did not feel motivated.

Scoring:

	Rarely or none of the time (less than 1 day)	Some or a little of the time (1-2 days)	Occasionally or a moderate amount of time (3-4 days)	All of the time (5-7 days)
--	--	---	--	----------------------------

Questions 5 & 8	3	2	1	0
All other questions	0	1	2	3

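### Protocol 7.7.2 sets no Step limit on its per-injection ISR proportion, although Step 3 injections have no one-week check; pooling the Steps is likely to bias it low, by an unknown amount

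*Protocol*

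**What the plan says.** Protocol 7.7.2 plans two ISR summaries that depend on which injections are counted. In the first, each participant's ISR for a given sign or symptom is "counted once under the maximum severity for all injection visits as well as by each successive injection". In the second, "we will report the proportion of injections (over all participants) that resulted in an ISR", with a 95% CI from a robust variance. Neither names a Step. The adjacent Protocol 7.7.1 sets the primary safety window as "from the initial injection to 48 weeks after the last injection among participants who receive at least one injection", which extends into Step 3.

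The two injection phases collect ISRs differently:

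- **Step 2.** Protocol 5.6 states that "all participants will have brief safety visits one week after each injection". Appendix II puts injections at Weeks 5, 9, 17, 25 and 33 and ISR evaluation at Weeks 6, 10, 18, 26 and 34.
- **Step 3, injection option.** Appendix IV marks both the CAB LA injection and the "ISR evaluation" at +8, +16, +24, +32, +40 and +48, and at early discontinuation. It has no column one week after an injection.

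On how long reactions last, Protocol 6.3 reports: "Median IM ISR durations were approximately 5 days for pain and erythema, and approximately 22 days for nodules".

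SAP v2.0 contains no per-injection ISR proportion. Its Appendix A treats ISRs as adverse events of special interest and states: "Listings will summarize Adverse events that occurred during Step 1 and/or Step 2 of the study".

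**The concern.** A proportion over injections is interpretable only if each injection has a similar chance of having its reaction recorded. Here a Step 2 injection is checked on schedule at about day 7. A Step 3 injection is next checked at about day 56, and the +48 injection has no later scheduled check. By day 56 most reactions should have resolved, so recording depends on recall or on a report between visits.

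Two outputs would be affected if the Steps are pooled. The overall proportion would probably be too low. The by-injection table could also drop from injection 6 onward because the check changed, and a reader could take that drop for improving tolerance of the injections. Separately, the SAP listing leaves Step 3 ISRs out altogether.

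**Working it through.** The documents give no figure for the ISR proportion. The only precision figures, the 95% CI half-widths at n = 50 in Protocol Table S1, reproduce with 1.96 × √(p(1−p)/50): 0.083, 0.111, 0.127, 0.136 and 0.139. They do not bear on this point.

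**1. Timing against duration.** The Step 3 gap is 8 × 7 = 56 days. That is 56/5 = 11.2 times the median for pain and erythema, and 56/22 = 2.5 times the median for nodules. If durations are exponential (an assumption), the share still present at day t is 2^(−t/median):

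| Reaction | Day 7 (Step 2) | Day 56 (Step 3) |
|---|---|---|
| Pain, erythema (median 5 days) | 38% | 0.04% |
| Nodules (median 22 days) | 80% | 17% |

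Step 2 also relies partly on recall for pain and erythema, but over one week rather than eight.

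**2. What the Step 3 evaluation can see.** Appendix IV does not say whether the evaluation comes before or after that day's injection. If before, it looks back 56 days; the +8 evaluation then concerns the Week 33 injection, already checked at Week 34, and the +48 injection is never checked on schedule. If after, it sees only reactions arising during the visit.

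**3. Step 3 share of injections.** Let f be the fraction of participants who take the Step 3 injections and n3 the number each receives. Assume five Step 2 injections for everyone. Then s = f·n3 / (5 + f·n3). Appendix IV marks six Step 3 injections. SAP 2.1 states five but lists six time points, so both counts are shown.

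| f | s, six injections | s, five injections |
|---|---|---|
| 0.25 | 1.5/6.5 = 23.1% | 1.25/6.25 = 20.0% |
| 0.5 | 3/8 = 37.5% | 2.5/7.5 = 33.3% |
| 1 | 6/11 = 54.5% | 5/10 = 50.0% |

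**4. Effect on the pooled proportion.** Let p be the per-injection rate, taken as equal in both Steps and fully captured in Step 2, and let d be the fraction of Step 3 reactions captured. The pooled value is p × (1 − s(1−d)), so the relative loss is s(1−d): nil at d = 1 and equal to s at d = 0. The documents give none of p, f and d. For illustration, with six injections:

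| Assumed p | f | d = 0 | d = 0.5 | d = 1 |
|---|---|---|---|---|
| 0.50 | 0.5 | 0.31 | 0.41 | 0.50 |
| 0.50 | 1 | 0.23 | 0.36 | 0.50 |
| 0.77 | 0.5 | 0.48 | 0.63 | 0.77 |
| 0.77 | 1 | 0.35 | 0.56 | 0.77 |

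The 0.77 borrows the figure in Protocol 6.3, which is the share of participants with any ISR and not a per-injection rate.

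**5. By-injection table.** With a constant true rate, rows 1 to 5 show p and rows 6 onward show d × p. At d = 0.5 the recorded rate halves at injection 6, whatever the uptake.

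**6. Size of the data.** SAP 6.4 records that enrollment stopped at nine. That allows at most 9 × 5 = 45 Step 2 injections and 9 × 6 = 54 Step 3 injections (45 on the count of five).

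**The case against.** The strongest reply is that pooling is read from silence. SAP v2.0 was revised for the Step 3 injection option and keeps the related analyses to Step 2 or earlier. Primary safety (8.1) ends by Week 41 or 8 weeks past the final Step 2 injection, the on-time analysis (12.4) counts up to five injections per participant, and Appendix A lists events from Steps 1 and 2 with no formal summaries. On the SAP's text the biased figure would not be produced. This stands as a limit on the point: a reader might infer that the plan expressly pools the Steps, and it does not. But the protocol wording covers every injection in every participant, and the SAP neither defines the analysis nor records that it was dropped.

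Second, there are other routes of capture. Participants have a 24-hour number and AEs of Grade 1 and above go on CRFs (Protocol 6.1). Interim visits for AEs are provided for (5.15), Appendix IV takes a medical history from +16 to +48, and Grade 3 or 4 ISRs go to the Clinical Management Committee (Appendix VI). This also stands. It makes zero capture implausible, though nothing makes capture equal to a one-week evaluation.

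Third, Step 3 CAB LA is optional, so 54.5% is an upper limit that needs everyone to take all six injections. This is correct, and it is why a range is given.

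Two stronger readings fail. A reader might infer that the tolerability endpoint is affected, but that endpoint is discontinuation before the full course (Protocol 7.2.1 and 7.7.4, SAP 8.2), and the ISR proportion is not an input to it. A reader might also take "A safety visit will follow each injection to ascertain pharmacokinetic-peak safety data, including injection site reactions" in Protocol 2.3 as a promise broken in Step 3, but the sentence sits in the Step 2 description.

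**Conclusion.** The point holds as an undefined scope combined with unequal ascertainment. As worded, Protocol 7.7.2 takes in Step 3 injections, whose reactions are next checked on schedule at about 56 days, or not at all after +48, against median durations of about 5 and 22 days. Pooling is likely to bias the proportion low and could create a fall after injection 5 that is not real.

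The direction is well supported if the true rate is similar in both Steps. The size is not known. The relative loss lies between nil and the Step 3 share of injections, 37.5% at half uptake and 54.5% at full uptake of six (33% and 50% on a count of five). That range treats Step 2 capture as complete. It is also firm that the SAP leaves this proportion unaddressed and omits Step 3 ISRs from its listing.

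**What to change.** - In Protocol 7.7.2 and the SAP, define the per-injection ISR proportion, its robust 95% CI and the by-successive-injection table on Step 2 injections only, the ones with a one-week evaluation. If the team does not intend to report the proportion, the SAP should record that it was dropped.
- Report Step 3 ISRs in a separate row, labelled as collected at 8-weekly visits or by spontaneous report.
- Extend the ISR listing in SAP Appendix A to Step 3.
- Reconcile the stated number of Step 3 injections in SAP 2.1 with the time points listed beside it and with Appendix IV, since the Step 3 denominator depends on it.

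The cost is wording, one table row and a longer listing covering at most 54 injections. No extra contact is asked for: a routine one-week contact after each Step 3 injection would be new data collection, beyond the as-needed contacts in Protocol 5.15.
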